This study is part of preliminary and pilot research to develop a technology-enhanced eLearning training in suicide safety planning that targets skill-building in general counseling skills to accompany a standard web-based didactic with skill demonstration in suicide safety planning. The training is designed to support acute medical care nurses to engage patients at-risk of suicide in collaborative and empathic suicide safety planning. Skill-building technologies include a chat bot called "Client Bot Emily" and an automated computer-based coding and computergenerated feedback report through a platform called Lyssn. This study is a formative evaluation of the technologyenhanced or eLearning approach. It includes assessment of training acceptability and engagement with the training components and technologies and the conduct of an end-of-evaluation focus groups with study nurses. Findings will be used to inform iterations to improve the acceptability of the training as well as to inform the implementation of the training and implementation of suicide safety planning with patients in a larger trial.

1.6) Study design. Provide a one-sentence description of the general study design and/or type of methodology.

Your answer will help HSD in assigning applications to reviewers and in managing workload. Examples: a longitudinal observational study; a double-blind, placebo-controlled randomized study; ethnographic interviews; web scraping from a convenience sample of blogs; medical record review; coordinating center for a multi-site study.

The study is an evaluation of an eLearning training approach that utilizes a pre-post training longitudinal design.

(1.7) Intent. Check all the descriptors that apply to your activity. You must place an "X" in at least one box.

This question is essential for ensuring that your application is correctly reviewed. Please read each option carefully.

Descriptor
1. Class project or other activity whose purpose is to provide an educational experience for the researcher (for example, to learn about the process or methods of doing research).
2. Part of an institution, organization, or program's own internal operational monitoring.
X 3. Improve the quality of service provided by a specific institution, organization, or program.

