Nurse training outcomes of general counseling skill quality and quality of safety planning will be assessed using standardized patient assessments. Nurses will complete four 30-minute role-plays over the course of the evaluation. These will be conducted by research staff/patient actors via Zoom, recorded, and assessed for general counseling skill quality using the Lyssn system. Pre- and post-training and follow-up role-plays will be assessed for fidelity to the safety planning intervention by the PI. Self-reported perception of skills will be assessed via survey at baseline, post-training and 6-months post-training using methods modified from training clinicians in evidence-based psychotherapy. Nurses will also complete **knowledge quizzes** of what is safety planning and how to do it.

Implementation barriers and facilitators will be assessed for both engaging in the training and using the skills learned with patients via nurse surveys at baseline, post-training and 6-months post-training as well as end-of-study focus groups. Questions will be designed using the TDF (e.g., beliefs about consequences, role & identity, environmental context & resources).

5.5 Data sources. For all types of data that will be accessed or collected for this research: Identify whether the data are being obtained from the subjects (or subjects' specimens) or whether they are being obtained from some other source (and identify the source).

If you have already provided this information in Question 5.1, you do not need to repeat the information here.

1. REDCap surveys

Research Electronic Data Capture (REDCap) is a HIPAA-compliant data capture system used by the UW and supported by UW's Institute of Translational Health Sciences. It will capture self-report survey data for this study, which are completed at baseline, post-training, and 6 months post-training.

2. Standardized patient role-play recordings & quality assessment

Nurses will be asked to complete four standardized patient role-plays with research staff or paid actors. These role-plays will be recorded. The Lyssn system will score the role-plays for general counseling skills. The PI will score the role-plays for quality of suicide safety planning. The results of scoring of role-plays will be kept on UW Medicine servers and in de-identified format.

3. Focus group recordings & transcripts

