c. If any identifiers will be obtained, indicate how the identifiers will be stored (and for which data). NOTE: Do not describe the data security plan here – that information is requested in section 9.6.
Identifiers will be stored with the data. Describe the data to which this applies:
Zoom audio/video recording will be stored on UW Medicine servers and accessible only by the research team. REDCap will store data with an email address, which is used to send out a survey link; however, downloaded data will be de-identified.
Identifiers and study data will be stored separately but a link will be maintained between the identifiers and the study data (for example, through the use of a code). Describe the data to which this applies:
Names and contact information will be stored separately from study data and will be maintained on UW Medicine servers. Nurses will have a study ID that is associated with their name in this file and then used to link study data in de-identified datasets.
Identifiers and study data will be stored separately, with no link between the identifiers and the study data. Describe the data to which this applies:
d. Research collaboration. Will individuals who provide coded information or specimens for the research also collaborate on other activities for this research? If yes, identify the activities and provide the name of the collaborator's institution/organization.
Examples include but are not limited to: (1) study, interpretation, or analysis of the data that results from the coded information or specimens; and (2) authorship on presentations or manuscripts related to this work.
No
5.7) Protected Health Information (PHI). Will participants' identifiable PHI be accessed, obtained, used, or disclosed for any reason (for example, to identify or screen potential subjects, to obtain study data or specimens, for study follow-up) that does not involve the creation or obtaining of a Limited Data Set?
PHI is individually identifiable healthcare record information or clinical specimens from an organization considered a "covered entity" by federal HIPAA regulations, in any form or media, whether electronic, paper, or oral. You must answer yes to this question if the research involves identifiable health care records (e.g., medical, dental, pharmacy, nursing, billing, etc.), identifiable healthcare information from a clinical department repository, or observations or recordings of clinical interactions.

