 - For materials that cannot be uploaded: upload screenshots or written descriptions that are sufficient to enable the IRB to understand the types of data that will be collected and the nature of the experience for the participant. You may also provide URLs (website addresses) or written descriptions below. Examples of materials that usually cannot be uploaded: mobile apps; computer-administered test; licensed and restricted standardized tests.
 - For data that will be gathered in an evolving way: This refers to data collection/questions that are not pre-determined but rather are shaped during interactions with participants in response to observations and responses made during those interactions. If this applies to the proposed research, provide a description of the process by which the data collection/questions will be established during the interactions with subjects, how the data collection/questions will be documented, the topics likely to be addressed, the most sensitive type of information likely to be gathered, and the limitations (if any) on topics that will be raised or pursued.

Use this text box (if desired) to provide:

- Short written descriptions of materials that cannot be uploaded, such as URLs
- A description of the process that will be used for data that will be gathered in an evolving way.
- The general content of questionnaires, surveys and similar instruments for which general approval is being sought. (See the **NOTE** bullet point in the instructions above.)

1. Standardized patient role-plays

Nurses will be invited to participate in 4 total 30-minute standardized patients role-plays. These roleplays are designed to provide opportunities to practice skills in suicide safety planning using general counseling skills and as assessments of skills for evaluation purposes. Scenarios will be of patients hospitalized for medical/surgical/trauma reasons of varying adult ages. Nurses will receive feedback from the Lyssn system on one of the role-plays as part of the training. The PI will also assess the quality using a measure of suicide safety planning as part of the formative evaluation on pre and post-training role-plays. The computer coded and human coded data will be maintained in study records ongoing in a de-identified format and used for evaluation and refinement of the training program.

2. REDCap surveys

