Nurses will be recruited on an ongoing basis, which is expected to take about two months. Nurses will engage in 3-4 hours of training that is expected to take about one month to complete. Enrolled nurses will also engage in evaluation activities that will take 3 hours total. In the first month, this includes several standardized patient role-plays of suicide safety planning and survey measures. Six months after the training is completed, nurses will be asked to complete a 6-month standardized patient role-play, 6-month follow-up survey, and participate in an end-of-study 1-hour focus group. Some role-plays will serve dual purposes as part of the training as well as to collect training outcome data.

Primary Outcomes

Acceptability. Nurse training and technology acceptability will be assessed using the System Usability Scale (SUS), open-ended questions, and a modified version of the Client Satisfaction Questionnaire-8 (CSQ-8) to assess nurse satisfaction with the training.

Training outcomes. Nurse training outcomes of general counseling skill quality and quality of safety planning will be assessed using standardized patient assessments. Nurses will complete four 30-minute role-plays over the course of the evaluation. These will be conducted by research staff or paid actors via Zoom, recorded, and assessed for general counseling skill quality using the Lyssn system. Pre- and post-training and follow-up role-plays will be assessed for fidelity to the safety planning intervention by the PI. Self-reported perception of skills will be assessed via survey at baseline, post-training and 6-months post-training using methods modified from training clinicians in evidence-based psychotherapy.

Secondary Outcomes

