Quantitative data will be viewed graphically and analyzed descriptively. Qualitative open-ended responses to questions will be summarized into common themes or content analyzed, as appropriate. Acceptability of the training will be supported by scores above 24 (indicates average of 3) on the CSQ-8 provider-version, above 67 on the SUS, and responses to open-ended questions based on relevant TDF constructs. Feasibility of the training will be supported by nurse use statistics collected by the computer technology and completion of all training parts (web-based didactic, Client Bot, and Lyssn feedback). Focus group qualitative data will be content analyzed according to TDF constructs.

3. Human Subjects Considerations

Inclusion/exclusion Criteria

All nurses working on participating units will be eligible for participation. There are no exclusion criteria. Nurses will opt into the study based on interest and willingness, including willingness to utilize a computer and the internet to participate in the web-based training activities.

Informed Consent

Informed consent may occur in person, by phone, or by videoconference. The PI/research staff will send the informed consent document to nurses ahead of time and then meet to go over and explain the study, review the consent form, and answer any questions. We will obtain a waiver of documentation of informed consent to facilitate virtual consent procedures. Nurses are expected to be literate in English at the high school level. They are also expected to be able to use computer, internet, REDCap technology as they routinely use these or similar systems in their routine work.

Risks Associated with Study Participation

Confidentiality. Nurses may be concerned that performance on the standard patient role-plays and responses to study surveys and focus group questions may be shared with colleagues or supervisors. **Observation/assessment burden.** Completing training and research tasks may be perceived as burdensome and nurses may experience some performance-related anxiety on the standardized patients. Nurses may experience some frustration interacting with the technology, which may depend on nurse computer technology literacy.

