Statistical Analysis Plan for eLearning for Suicide Prevention, ID: STUDY00013577, NCT05178121

We will examine descriptive statistics for all outcomes, including frequencies for categorical variables and the mean, standard deviation, and confidence intervals based on the standard error of the mean for variables observed across timepoints.

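### The analysis plan commits to summaries at each timepoint but to none of within-nurse change, and the role-play called pre-training is scheduled after the web didactic

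*Combined protocol and SAP*

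**What the plan says.** The SAP is one sentence. It covers all outcomes descriptively: frequencies for categorical variables, and the mean, standard deviation and "confidence intervals based on the standard error of the mean for variables observed across timepoints". The Plan of Analysis in section 2 of the Data and Safety Monitoring Protocol (DSMP) states: "Quantitative data will be viewed graphically and analyzed descriptively". It then gives the acceptability and feasibility criteria. Neither text names a change score or a paired difference.

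Section 1.6 of the IRB protocol says that the study "utilizes a pre-post training longitudinal design". Under section 5.6c each nurse has a study ID that is "then used to link study data in de-identified datasets". Section 5.4 gives repeated measurement: "Self-reported perception of skills will be assessed via survey at baseline, post-training and 6-months post-training". The DSMP lists counseling skill quality, safety-planning quality and self-reported skills under Primary Outcomes, next to acceptability.

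On role-plays, section 5.4 says "Pre- and post-training and follow-up role-plays will be assessed for fidelity", and the DSMP repeats it: "Pre- and post-training and follow-up role-plays will be assessed for fidelity to the safety planning intervention by the PI". Section 5.14 describes the PI's scoring "as part of the formative evaluation on pre and post-training role-plays". The Attachment on Nurse Study Activities & Remuneration places the web didactic at activity 2 and the four role-plays at activities 3, 5, 7 and 9. It labels the data from the first role-play as post-web-training. Section 5.1 counts the hour of didactics among the training activities.

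**The concern.** A pre-post study of the same nurses exists to show how each nurse moved. Means and intervals at each timepoint show where the group stood, but not how precisely the average change is estimated, nor whether most nurses changed or only a few. The findings are meant to inform a larger trial, and several of the repeated measures carry the primary label. Unless the change summary and its reference timepoint are fixed in advance, both can be chosen after the data are seen.

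The role-play label adds a second problem. If the first role-play follows the didactic, a contrast reported as pre-post leaves out whatever the didactic itself achieved, and a reader would take it for the effect of the whole training.

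The set of nurses may also differ between timepoints. DSMP section 3 lets nurses skip survey questions and end role-plays, so timepoint means can shift through composition alone. Paired summaries that state the number of pairs would make this visible.

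**Working it through.** The documents give no sample-size or precision calculation, so there is no figure to reproduce.

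**Step 1: what timepoint summaries leave open.** The inputs are:
- n = 20, the stated maximum (sections 2.1 and 2.8).
- r, the within-nurse correlation, is not in the documents. It is assumed at 0, 0.3, 0.5 and 0.7.
- SDs are assumed equal at the two timepoints, and results are in units of that SD.
- The confidence level is assumed to be 95%, with t(0.975, 19) = 2.093 and √20 = 4.472.

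The half-width for one timepoint mean is 2.093 / 4.472 = 0.468 SD, whatever r is.

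The SD of individual change is √(2(1 − r)). The half-width for mean change is 2.093 × that SD / 4.472.

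| assumed r | SD of change | 95% half-width for mean change |
|---|---|---|
| 0 | √2.0 = 1.414 | 0.662 |
| 0.3 | √1.4 = 1.183 | 0.554 |
| 0.5 | √1.0 = 1.000 | 0.468 |
| 0.7 | √0.6 = 0.775 | 0.363 |

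All four rows are compatible with identical timepoint means, SDs and intervals. With fewer complete pairs the same range of r gives 0.783 to 0.429 SD at n = 15 (t = 2.145) and 1.012 to 0.554 SD at n = 10 (t = 2.262).

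**Step 2: the reference role-play.** The schedule runs: baseline survey (activity 1), web didactic and demonstration (2), role-play (3), chat bot (4), role-play (5), Lyssn feedback (6), post-training role-play (7), post-training survey (8), 6-month role-play (9), 6-month survey (10), focus group (11). Since section 5.1 counts the didactic as training, no role-play precedes all training. Only the survey is a true pre-training measure. The pre-training wording in sections 5.4 and 5.14 and in the DSMP therefore does not fit the schedule.

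**Step 3: scoring of the 6-month role-play.** Section 5.4 and the DSMP Primary Outcomes include the follow-up role-play. Section 5.14 names pre- and post-training role-plays and does not mention follow-up. Section 5.5 has the PI score the role-plays without restriction. DSMP section 4 says that some are coded. Section 5.14 omits the follow-up but does not exclude it.

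**The case against.** The strongest reply is that this is a formative evaluation of up to 20 nurses, aimed at acceptability, engagement and implementation. It states no hypothesis about change. Its only decision criteria are CSQ-8 above 24, SUS above 67, use statistics and completion of the training parts, and none of these needs a change score. The SAP's list of statistics is introduced as inclusive, and the DSMP plans graphs, so individual differences and trajectories are already permitted. All of that stands. It makes the gap a missing commitment and not an error, and it is why no hypothesis test is called for. But training outcomes are listed as primary, and a plan that merely permits a summary does not settle which contrast will be reported.

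It may also be said that the post-didactic reference is deliberate, because the eLearning Approach attachment places the two technologies after the didactic. That is plausible. The reference would then be sound and only its label wrong.

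Three stronger readings are tempting, and the documents do not support them:
- A reader might infer that the planned intervals are invalid. They are valid for each timepoint mean.
- A reader might infer that change will be assessed as if the timepoints were independent samples. At n = 20 that would give 2.024 × √(2/20) = 0.640 SD whatever r is, but no document proposes it.
- A reader might infer that section 5.14 rules out PI scoring at 6 months. It does not say so, and section 5.4 and the DSMP expressly include that role-play.

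**Conclusion.** The point holds on two counts and should be fixed. First, the plan commits to no summary of within-nurse change in a linked pre-post design, and the missing precision cannot be rebuilt from what it does promise. In the illustration the half-width at r = 0 is 0.662 / 0.363 = 1.8 times that at r = 0.7. This rests on an assumed r, equal SDs, a 95% level and the maximum of 20 complete pairs; the actual r will be known only from the data. Second, the pre-training label conflicts with the schedule, in which every role-play follows the didactic. That count rests on the text alone.

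The difference over 6-month fidelity scoring is a minor wording point.

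**What to change.** Keep the timepoint summaries and add to the SAP:

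- For each outcome measured at a reference timepoint and later, report the mean within-nurse change, its SD, a t-based 95% CI from the individual differences and the number of nurses with both values, and plot individual trajectories. No hypothesis test is needed.
- Use baseline as the reference only for survey items asked at baseline (self-reported skills, motivation, TDF constructs). For items first asked after training (acceptability, self-reported technology use), give timepoint values and, if wanted, change from post-training to 6 months. For the knowledge quizzes, name the reference; the schedule first collects them inside the didactic.
- State that restricting to nurses with both values removes shifts due to changing composition, but not selection in who completes.

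In the protocol and DSMP, reconcile the pre-training wording in section 5.4, section 5.14 and the DSMP Primary Outcomes with the activity schedule. If the schedule stands, label the role-play contrast as change from the post-didactic role-play and state that it excludes any didactic effect. Align section 5.14 with section 5.4 and the DSMP on the follow-up role-play.

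The cost is a few sentences of SAP text, these wording corrections and trivial extra analysis. The change summaries need no new data.
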